Study Centre(s):	University of Applied Sciences and Arts Southern Switzerland Physiotherapy Graubünden Rehabilitation Research Laboratory 2rLab Rehabilitation and Exercise Science Group [name]
Statistical Considerations:	
The effectiveness of repeated cold and hot water baths on recovery and performance is tested by:
 
Repeated measures analysis of variance (MANOVA)
 
Factors:
 
• Protocol• Task (repeated cold water immersion vs. repeated hot water immersion, repeated cold water immersion vs. control group, repeated hot water immersion vs. control group, repeated cold water immersion vs. passive group with hypoxia conditions, repeated hot water immersion vs. passive group with hypoxia conditions)• Time (these factors are measured immediately after cooling/warming and 24 hours, 48 hours and 72 hours after the interventions). 
The significance level is set at $P < 0.05$, and the statistical data analysis is performed with SPSS 27.

SUPSI

GCP Statement:	This study will be conducted in compliance with the protocol, the current version of the Declaration of Helsinki, the ICH-GCP or ISO EN 14155 (as far as applicable) as well as all national legal and regulatory requirements.
-----------------------	---

SUPSI

ABBREVIATIONS

AE	Adverse Event
BASEC	Business Administration System for Ethical Committees, (https://submissions.swissethics.ch/en/)
CA	Competent Authority
CEC	Competent Ethics Committee
CK	Creatine Kinase
CRF	Case Report Form
CRP	C-reactive protein
ClinO	Ordinance on Clinical Trials in Human Research (in German: KlinV, in French: OClin, in Italian: OSRUm)
eCRF	Electronic Case Report Form
CTCAE	Common terminology criteria for adverse events
DSUR	Development safety update report
GCP	Good Clinical Practice
IB	Investigator's Brochure
Ho	Null hypothesis
H1	Alternative hypothesis
HRA	Federal Act on Research involving Human Beings (in German: HFG, in French: LRH, in Italian: LRUm)
IL6	Interleukin 6
IMP	Investigational Medicinal Product
IIT	Investigator-initiated Trial
ISO	International Organisation for Standardisation
ITT	Intention to treat
MD	Medical Device
MedDO	Medical Device Ordinance (in German: MepV, in French: ODim)
MVIC	Maximum voluntary isometric muscle contraction
PI	Principal Investigator
SDV	Source Data Verification
SOP	Standard Operating Procedure
SPC	Summary of product characteristics
SS Test	Pregnancy test

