9. STUDY ASSESSMENTS

9.1 Study flow chart(s) / table of study procedures and assessments

The test subject information is sent to the test subjects' homes in advance or given to them personally

1. Subject Information & Informed Consent

30 min (questions and ambiguities will be discussed individually)

2. Preparation of the test person

15 min

3. Executing the test protocol

SUPSI

Test protocol: Time required – maximum 255 min			
Cold Water Immersion vs. Hot Water Immersion vs. Hypoxia Group vs. Passive Control Group			
Cold water immersion 1.) Baseline Informed consent, written consent, review of inclusion/exclusion criteria, health questionnaire, pregnancy test Heart rate Skin/ core body temperature Oxygen saturation (blood, muscle) Inflammation parameters VAS & BORG thermal comfort and thermal sensation US 3 x Vertical Jumps 3 x MVIC =30 min	Hot water immersion 1.) Baseline Informed consent, written consent, review of inclusion/exclusion criteria, health questionnaire, pregnancy test Heart rate Skin/core body temperature Oxygen saturation (blood, muscle) Inflammation parameters VAS & BORG thermal comfort and thermal sensation US 3 x Vertical Jumps 3 x MVIC =30 min	Hypoxia Intervention 1.) Baseline Informed consent, written consent, review of inclusion/exclusion criteria, health questionnaire, pregnancy test Heart rate Skin/core body temperature Oxygen saturation (blood, muscle) Inflammation parameters VAS & BORG thermal comfort and thermal sensation US 3 x Vertical Jumps 3 x MVIC =30 min	Passive Control Intervention 1.) Baseline Informed consent, written consent, review of inclusion/exclusion criteria, health questionnaire, pregnancy test Heart rate Skin/core body temperature Oxygen saturation (blood, muscle) Inflammation parameters VAS & BORG thermal comfort and thermal sensation US 3 x Vertical Jumps 3 x MVIC =30 min
2.) Jump protocol 5 x 20 max vertical jumps after 30sec Heart rate Skin/ core body temperature	2.) Jump protocol 5 x 20 max vertical jumps after 30sec Heart rate Skin/ core body temperature	2.) Jump protocol under hypoxia 5 x 20 max vertical jumps after 30sec Heart rate Skin/ core body temperature	2.) Jump protocol 5 x 20 max vertical jumps after 30 sec Heart rate Skin/ core body temperature

SUPSI

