11. STATISTICAL METHODS

11.1 Hypothesis

Jump height (cm)

H0 The jump height is not increased by the hot water immersion compared to the cold water immersion, hypoxia group and passive control group during a 72-hour recovery phase.

H1 The jump height is increased by the hot water immersion compared to the cold water immersion, hypoxia group and passive control group during 72 hours.

MVIC (kg)

H0 MVIC performance is not increased by hot water immersion compared to cold water immersion, hypoxia group, and passive control group during a 72-hour recovery period.

H1 The MVIC efficiency is increased by hot water immersion compared to cold water immersion, hypoxia group and passive control group during 72 hours.

Muscle swelling (mm)

H0 Muscle swelling is not increased by hot water immersion compared to cold water immersion, hypoxia group, and passive control group during a 72-hour recovery period.

H1 Muscle swelling is increased by hot water immersion compared to cold water immersion, hypoxia group and passive control group for 72 hours.

Blood oxygen saturation (%)

H0 Blood oxygen saturation is not increased by hot water immersion compared to cold water immersion, hypoxia group and passive control group during a 72-hour recovery period.

H1 The oxygen saturation of the blood is increased by the hot water immersion compared to the cold water immersion, hypoxia group and passive control group during 72 hours.

Oxygen Saturation Muscle (%)

H0 Oxygen saturation of the thigh muscle is not increased by hot water immersion compared to cold water immersion, hypoxia group and passive control group during a 72-hour recovery period.

H1 The oxygen saturation of the thigh muscle is increased by hot water immersion compared to cold water immersion, hypoxia group and passive control group during 72 hours.

Heart rate (b/min)

H0 The heart rate is not increased by the hot water immersion compared to the cold water immersion, hypoxia group and passive control group during a 72-hours of recovery.

H1 Heart rate is increased by hot water immersion compared to cold water immersion, hypoxia group and passive control group during 72 hours.

SUPSI

Skin temperature (°C)

H0 Skin temperature is not increased by hot water immersion compared to cold water immersion, hypoxia group and passive control group during a 72-hour recovery period.

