H1 Thermal comfort and temperature perception are increased by hot water immersion compared to cold water immersion, hypoxia group and passive control group during 72 hours.

A 2-factor analysis is carried out.

Factor 1: Intervention (cold water immersion vs. hot water immersion vs. hypoxia group vs. Passive Control Intervention)

Factor 2: Time (Baseline, 0, 24 hours, 48 hours, 72 hours)

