11.4.2 Primary Analysis

The statistical data analysis will be carried out by [name] once the data collection for the entire project has been completed.

Repeated measures analysis of variance (MANOVA)

2 factors:

Factor 1: Intervention (cold water immersion vs. hot water immersion vs. hypoxia group vs. passive control intervention)

Factor 2: Time (Baseline, 0, 24 hours, 48 hours, 72 hours)

The significance level is set at $P < 0.05$, and the statistical data analysis is carried out with SPSS 27.

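### Baseline is a level of the Time factor and never a covariate, and the deciding term is unnamed; if that term is the Intervention main effect, the effect is diluted to four fifths and most of the baseline-adjusted information is lost.

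*Combined protocol and SAP*

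**What the plan says.** Section 11.4.2 names one method, "Repeated measures analysis of variance (MANOVA"), with two factors. The first is the four-arm comparison, "Factor 1: Intervention (cold water immersion vs. hot water immersion vs. hypoxia group vs. passive control intervention"). The second is "Factor 2: Time (Baseline, 0, 24 hours, 48 hours, 72 hours"). The threshold is given as "The significance level is set at $P < 0.05". Section 11.1 sets the same two factors after the hypotheses ("A 2-factor analysis is carried out"). Neither section names a covariate, a change score or the model term that decides, and section 11.4.3 offers no secondary analysis.

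The synopsis (Statistical Considerations) defines the factor differently: "Time (these factors are measured immediately after cooling/warming and 24 hours, 48 hours and 72 hours after the interventions"). That list has four times and no baseline.

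The hypotheses in 11.1 all share one form. For jump height: "The jump height is increased by the hot water immersion compared to the cold water immersion, hypoxia group and passive control group during 72 hours". No time point or model term is specified.

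The flow chart in 9.1 puts ultrasound, jumps and MVIC in the baseline step of all four arms, before the jump protocol: "3 x Vertical Jumps 3 x MVIC =30 min". Sections 5.1 and 9.2.1 list a pre-intervention reading for muscle swelling but only post-intervention times for jump height and MVIC.

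**The concern.** The baseline reading precedes both the exercise and the allocated treatment, so randomised arms can differ there only by chance. As a level of Time, it enters the Intervention main effect as one fifth of an average, at a time when no effect is possible. Stable differences between women also stay in the error term for that test. As a covariate, the same reading would remove part of that variation.

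With 8 to 15 women per arm the loss could be large. Its size depends on which term decides, and the plan leaves that open. The synopsis adds a third possibility: four post-treatment times, with baseline not used at all.

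**Working it through.** **Inputs from the documents.** Four arms; alpha 0.05; five Time levels. Section 11.2 gives 33 evaluable and 40 enrolled women, and section 6.1 gives 60. With equal arms (the allocation ratio is not stated) that is 33/4 = 8.25, 40/4 = 10 and 60/4 = 15 per arm. The figure of 33 cannot be rebuilt, because the effect size and the G*Power settings are not in the text and the figure is not shown.

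**Assumptions.** Equal SD at each time (set to 1); equal correlation rho between times, 0.5 to 0.9; one arm shifted by d at all four post-treatment times, the other three equal.

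**Step 1: dilution.** The main effect averages (0 + d + d + d + d)/5 = 0.8d. This is exact for a constant effect.

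**Step 2: information on d**, apart from a common factor for n:

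- Main effect over five times: 0.64/[(1 + 4rho)/5]
- Intervention x Time, along the constant-effect contrast: 0.8/(1 - rho)
- Baseline-adjusted mean of the four post values: 4/[(1 - rho)(1 + 4rho)]

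Dividing the first two by the third, the main effect keeps 0.8(1 - rho) and the interaction contrast keeps 0.2(1 + 4rho).

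| rho | main effect keeps | interaction contrast keeps |
|---|---|---|
| 0.5 | 40% | 60% |
| 0.7 | 24% | 76% |
| 0.8 | 16% | 84% |
| 0.9 | 8% | 92% |

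The main effect loses more than half once rho exceeds 0.375. On the synopsis reading (four post times, baseline unused) nothing is diluted, but only 60%, 37%, 25% and 12% is kept.

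**Step 3: power** from the noncentral F distribution. With one arm in four shifted, the between-arm sum of squares is 0.75d². For d = 0.8, n = 8, rho = 0.7:

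- Main effect: 8 x 0.75 x 0.64²/0.76 = 3.23 on 3 and 28 df, power 26%
- Intervention x Time: 0.6 x 8 x 0.64/0.3 = 10.24 on 12 and 112 df, power 47%
- Change from baseline, mean of the four post values: 8 x 0.75 x 0.64/0.375 = 10.24 on 3 and 28 df, power 71%
- Baseline as covariate: 8 x 0.75 x 0.64/0.285 = 13.47 on 3 and 27 df, power 83%

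The second and third lines have the same noncentrality. The rise from 47% to 71% comes only from using 3 rather than 12 numerator df; the covariate adds the rise from 71% to 83%.

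| n per arm, rho | main effect | interaction (12 df) | change (3 df) | covariate (3 df) |
|---|---|---|---|---|
| 8, 0.5 | 32% | 28% | 47% | 70% |
| 8, 0.7 | 26% | 47% | 71% | 83% |
| 8, 0.8 | 24% | 69% | 88% | 93% |
| 15, 0.7 | 49% | 83% | 96% | 99% |

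**Step 4: an effect that varies over time.** Simulation, 1,500 runs, n = 10 per arm, rho = 0.8, mean post-treatment effect 0.7 SD:

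| effect | covariate | main effect | interaction, Greenhouse-Geisser | interaction, Pillai |
|---|---|---|---|---|
| constant | 92% | 23% | 65% | 51% |
| peaking at 24-48 h | 91% | 23% | 98% | 90% |

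**Step 5: precision of a pairwise difference**, 24-72 h mean, n = 8. The 95% half-width is t x sqrt(2V/8), with V = (1 + 2rho)/3 + 1 - 2rho for change from baseline (28 df, t = 2.048) and V = (1 + 2rho)/3 - rho² for the covariate (27 df, t = 2.052).

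| rho | change from baseline | covariate |
|---|---|---|
| 0.5 | 0.84 SD | 0.66 SD |
| 0.7 | 0.65 SD | 0.57 SD |
| 0.8 | 0.53 SD | 0.49 SD |

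**The case against.** A reader might infer that having baseline in the Time factor dilutes the effect and wastes most of the precision whichever term is tested. That does not follow. Intervention x Time compares changes from baseline, so it dilutes nothing, and its constant-effect contrast keeps 60-92% of the information. It can match or beat the covariate analysis when the effect varies over time. For a recovery trial with baseline among the times, the interaction is also a natural reading of the plan. The analysis is a valid one for change; what is at issue is efficiency and an unnamed test.

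A reader might also credit the whole rise from 47% to 83% to the covariate, or set the covariate's interval against raw post-treatment means (half-width 0.92 to 0.95 SD at rho 0.7 to 0.8, n = 8). Neither comparison is fair. The first is partly 12 df against 3. The second ignores the change contrast that the planned model can already supply, against which the gain is 0.08 SD at rho 0.7 and 0.04 SD at rho 0.8.

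Finally, the documents give no correlation or SD, so how far women differ at baseline is not established.

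All of this stands, and it confines the large loss to the main effect. It does not settle the plan. The deciding term is still unnamed, the hypotheses about an overall difference across the recovery period read most directly onto the main effect, and a 12-df omnibus test does not estimate hot water against each comparator.

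**Conclusion.** The point holds in a conditional form. Two things are certain from the text: baseline is collected in all four arms but never used as a covariate, and the synopsis disagrees with sections 11.1 and 11.4.2 on whether it belongs to Time. The deciding term is also unspecified.

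The consequence depends on that term. For the main effect it is serious: an estimate of 4/5 of a constant effect, and 60-92% of the adjusted information lost over rho 0.5 to 0.9. For the interaction it is moderate when the effect is sustained, chiefly because of the 12 df, and it may vanish when the effect varies over time. The claim that true differences will probably be missed is therefore supported only for the main effect.

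The 4/5 factor needs only a constant effect. The other sizes rest on the assumed rho, equal SDs, equal arms and effect shape.

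**What to change.** 1. Reconcile the Time factor in the synopsis with 11.1 and 11.4.2, and add the baseline reading to the jump-height and MVIC entries in 5.1 and 9.2.1 so that they match the flow chart.
2. Take Baseline out of Time. For jump height, MVIC, muscle swelling and the other outcomes with a baseline reading, model the four post-treatment values with arm, time, arm x time and the woman's own baseline as covariate (ANCOVA or a repeated-measures mixed model). Keeping arm x time preserves sensitivity to effects that vary over the 72 hours.
3. Name the deciding between-arm contrast or contrasts, with the time point or average they refer to, and report baseline-adjusted differences with 95% confidence intervals.

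The cost is plan wording and about one degree of freedom per model. No new measurement is needed.

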Background and Rationale:	
External cooling applications have been known and used in elite sports for years. Hot water baths have also been used for several years, both in sports and in the medical field. These non-invasive interventions are becoming increasingly popular, as hydrotherapy is said to have positive effects before and after sporting activity. For example, hydrotherapy is said to contribute to improved regeneration after sporting activity. Literature on this topic is already available. However, the results are inconclusive and more randomised controlled trials need to be conducted to clarify the results.
 
In addition to the investigations between hot and cold water, recent research in the field of sports shows that exposure to extreme environments (e.g. stays at altitude) can impair not only cognitive function but also physical performance and the perception of pain. To the authors' knowledge, there is limited literature on how physical performance affects recovery under hypoxia conditions.
 
Numerous studies have already looked at cold water baths and training under hypoxia conditions to investigate the effects on recovery. The scientific results do not yet allow a clear recommendation for hydrotherapy as an accelerator of recovery. The extent to which training under hypoxia influences regeneration has only been minimally investigated. Further, randomised studies are needed to investigate the effects of hydrotherapy and hypoxia on the ability to regenerate.

Objective(s):	
The aim of this study is to investigate the effectiveness of repeated cold and hot baths and provide new insights into the appropriate use of this form of application. The study investigates the effect of repeated cold and hot water baths on the maximum voluntary isometric muscle contraction of the thigh muscles, vertical jump height, inflammation parameter from venous blood, muscle swelling and the evaluation of subjective muscle soreness in the legs and perceived general exhaustion during 72 hours of recovery. As an exhaustive measure, the subjects must complete a total of 5 x 20 maximum vertical jumps.

SUPSI

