Outcome(s):	
Primary outcomes
 
Physiological measurements
 
• Jump height measurement (cm)• Maximum Voluntary Isometric thigh Contraction (kg)• Muscle swelling (mm)• Blood oxygen saturation (%)• Oxygen saturation of the muscles (%)• Heart rate (bpm)• Skin temperature (°C)• Core Body Temperature (°C)• Inflammation parameters: IL6 (pg/ml), CRP (mg/dl), creatine kinase (U/L) 
Psychological measurements
 
• Dyspnea questionnaire (mod. Borg scale)• Exhaustion questionnaire (Borg scale)• Subjective muscle soreness (VAS scale)• Thermal comfort and thermal sensation 
Secondary outcomes: none

Study design:	Randomised, controlled trial

SUPSI

Inclusion / Exclusion criteria:	
Inclusion Criteria
 
• Young, healthy women aged 18 – 35 years• No surgical interventions on the musculoskeletal system in the trunk area and lower extremities• Anticonceptives 
Exclusion criteria
 
• Current injuries of any kind affecting the trunk and/or lower extremities• Injuries to the torso and/or lower extremities that occurred less than one year ago• Injuries to the trunk and/or lower extremities that occurred more than one year ago and are still causing symptoms• Fear of cold and/or hot water intervention• Fear of hypoxia• Taking medication of any kind (even self-purchased)• Pacemakers & cardiac arrhythmias• Known circulatory problems• Positive pregnancy test• Diagnosed skeletal static deviations• Appendectomy less than 2 years ago• Raynaud's syndrome
--	--

SUPSI

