To the knowledge of the authors, however, there are only limited studies investigating physiological parameters of recovery in laboratory conditions. In addition, various patient groups also suffer from lung dysfunction (such as COPD) and are therefore at least partially under hypoxic conditions. With this study, we can contribute to understanding the psychophysiological responses of recovery under hypoxia.

Aim of the study

In this project, the effect of repeated cold water immersions (10 °C for 10 min and again after 2 hours), repeated hot water immersions (40°C for 10 min and again after 2 hours), a hypoxia group (jump protocol under hypoxia and subsequent supine position for 10 min), and a passive control group (lying still in a supine position for 10 min) will be compared. The influence of these interventions and their effects will be investigated after a maximum jump load (5 x 20 jumps). The objective recovery parameters are vertical jump height, MVIC of the ventral thigh muscle, heart rate, muscle swelling, skin and core body temperature, measurement of inflammatory parameters, oxygen saturation of the blood and thigh muscles. Subjective recovery parameters are the local muscle soreness data, the general exhaustion and shortness of breath as well as information on thermal comfort and temperature sensation. The parameters are measured directly and 24, 48 and 72 hours after exercise. The aim is to determine the effects of thermotherapy in order to be able to make recommendations. The current state of scientific knowledge calls for further studies to substantiate or refute effects that have already been established.

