4. STUDY OBJECTIVES

4.1 Overall Objective

In this study, the effect of body cooling for a maximum of 10 minutes and renewed cooling or warming after 2 hours on the subjective muscle soreness and general exhaustion data as well as the objectively measurable MVIC of the ventral thigh muscles and the maximum vertical jump height after exhausting physical exertion will be investigated. In addition to the parameters already mentioned, the heart rate, skin temperature, core body temperature, muscle swelling and oxygen saturation of the thigh muscles as well as inflammation parameters of the blood are to be determined. The effects of thermal application will be contrasted with a hypoxia group and a passive control group and compared directly, 24 hours, 48 hours and 72 hours after the interventions. The aim is to substantiate the state of scientific knowledge and to provide therapists and physicians with further insights. This study can benefit all those who work with amateur and elite athletes.

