5. STUDY OUTCOMES

5.1 Primary Outcome

Jump height measurement

The jump height after exercise is determined using a specially designed jump height measuring plate (Just Jump Plate, Probotics Inc., Huntsville, USA). The test subjects assume a standing position on the plate. They are allowed to start from a squatting position to measure the jump height (countermovement jump). The arms must be positioned at the hips during the entire movement. The measurement take place directly, 24 hours, 48 hours and 72 hours after the intervention.

Muscle activity (MVIC)

MVIC is performed on the Cor 1 – ergometer chair for biomechanical measurements V1.0 and is expressed in kg (www.otbioelettronica.it). The conduction velocity is measured using the surface electromyogram system EMG-USB2 from OT Bioelettronica ([otbioelettronica.it](http://www.otbioelettronica.it)), bandpass filtered between 10-750Hz and rectified (full-wave rectify). MVIC is measured on the Cor 1 ergometer chair in 90° knee flexion. The raw data of muscle activity to measure conduction velocity is processed using OT Bioelettronica software (MISO II). The electrodes are placed according to the guidelines of Barbero et al. (2012) "Atlas of Muscle Innervation Zones". The measurement takes place immediately, 24 hours, 48 hours and 72 hours after the intervention.

Muscle swelling

Muscle swelling of the thigh is measured by ultrasound imaging (MyLabClassC, Esaote, Genoa, Italy). The images were evaluated using the OsiriX DICOM viewer software (OsiriX, Pixmeo SARL, Switzerland). The measurement takes place before, directly, 24 hours, 48 hours and 72 hours after the intervention.

Oxygen saturation of the blood

The oxygen saturation of the blood is measured with a portable pulse oximeter with a finger clip probe (Nonin 7500, Nonin medical B.V., Plymouth, USA). This measurement takes place during the baseline measurements as well as during the jump protocol.

Figure: Measurement of the oxygen content of the blood

Oxygen saturation of the muscle

The oxygen saturation (%) of the thigh muscles is measured with the tissue oxygenation monitor using near-infrared spectroscopy (moorVMS-NIRS, moor instruments, www.moore.co.uk). The measurement is non-invasive and takes place via near-infrared light. The sensors are fixed around the corresponding

SUPSI

muscles. The muscle oxygen saturation measurement is taken directly and 24, 48 and 72 hours after the intervention.

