Figure: Measurement of the oxygen saturation of the muscle

Heart rate

The heart rate is determined by means of a heart rate monitor with a chest strap (Polar T31, Polar Inc. Kempele, Finland). Blood pressure and heart rate are measured directly and 24, 48 and 72 hours after the intervention.

Skin temperature

Skin temperature is measured via the iButton system (www.ibuttonlink.com). The self-adhesive sensors transmit the information about the skin temperature wirelessly to a computer. Furthermore, the skin temperature is recorded using a thermal imaging camera (A655 sc series, FLIR, InfrarotTec Systems, Ranstadt, Germany). The Skin temperature is measured directly and 24, 48 and 72 hours after the intervention. The iButtons are attached to the following locations using a tape strip: centre of the shoulder blade, neck (6th cervical vertebra), back of the hand, centre of the shin and centre of the thigh. The iButtons are removed from the affected areas during the cold water bath or hot water bath and then reattached.

Core Body Temperature

The core body temperature is determined via the e-Celsius® performance (<https://www.bodycapmedical.com>). With the help of this ingestible capsule, the core body temperature is continuously monitored, recorded and transmits the data wirelessly to a monitor (BodyCAP medical, Hérouville Saint-Clair, France). Core body temperature is measured directly and 24, 48 and 72 hours after the intervention.

Inflammation parameters

The measurement of inflammatory parameters such as creatine kinase (CK), interleukin 6 (IL6) or C-reactive protein (CRP) is carried out via a venous blood sample of approx. 6ml (Accutrend, Roche Diagnostic, Rotkreuz, Switzerland & Reflotron, Roche Diagnostic, Rotkreuz, Switzerland). The measurement takes place directly, 24 hours, 48 hours and 72 hours after the intervention by trained specialists.

SUPSI

Subjective information on breathlessness

The subjects indicate their subjective feeling of breathlessness on a modified BORG scale (0 – 10). The scale will be scaled from "0" (no shortness of breath at all) to "10" (maximum breathlessness). The measurement takes place before the intervention.

Subjective information on general exhaustion

The subjects indicate their subjective general feeling of exhaustion on a BORG scale (6 – 20). The scale will be scaled from "6" (very, very light load) to "20" (very, very strenuous load). The measurement takes place before the intervention.

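### Every listed outcome is primary and no lead outcome, contrast, time point or multiplicity rule is set, so the stated 5% level and 80% power do not describe the set of primary hypotheses

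*Combined protocol and SAP*

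**What the plan says.** - **Error level.** Section 11.4.2 plans a repeated-measures analysis of variance, with MANOVA added in brackets. The factors are intervention (four groups) and time (baseline, 0, 24, 48 and 72 h). It then states "The significance level is set at $P < 0.05$, and the statistical data analysis is carried out with SPSS 27". No adjustment, testing order or split of the 5% is given.
- **Status of outcomes.** The synopsis, 4.2 and 5.1 list nine physiological and four psychological items, all primary. The synopsis adds "Secondary outcomes: none". Sections 4.3, 5.2, 5.3 and 11.4.3 are likewise empty.
- **Hypotheses.** Section 11.1 has 13 pairs of H0 and H1, one per item. Three blood markers share one pair and two thermal scales share another, with no rule if they disagree.
- **Contrasts.** Section 11.1 sets hot water against the other three groups. The synopsis (Statistical Considerations) lists five pairwise comparisons, among them "repeated cold water immersion vs. control group, repeated hot water immersion vs. control group", and ranks none.
- **Narrower lists.** The synopsis Objective names MVIC, "vertical jump height, inflammation parameter from venous blood, muscle swelling and the evaluation of subjective muscle soreness in the legs and perceived general exhaustion". Section 4.1 opens with soreness, exhaustion, MVIC and jump height and then continues: "In addition to the parameters already mentioned, the heart rate, skin temperature, core body temperature, muscle swelling and oxygen saturation of the thigh muscles". Sections 4.2, 5.1 and 11 keep neither order, and 3.1 puts all on one footing: "The objective recovery parameters are vertical jump height, MVIC of the ventral thigh muscle, heart rate, muscle swelling, skin and core body temperature".
- **Power.** The readable text of 11.2 gives 80% power at 5% for one parameter difference and does not name the outcome.

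**The concern.** Followed as written, the plan lets a primary claim rest on whichever of the 13 hypotheses reaches P < 0.05, at whichever contrast and time point.

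The alternatives in 11.1 also do not point one way. Hot water is predicted to raise jump height and MVIC, but also swelling, inflammation, exhaustion and soreness. Significant results on different outcomes would mean opposite things for recovery, and no rule says which one answers the question.

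The opportunity to choose after seeing data is practical. Section 11.4.4 has the data analysed in stages, and 12.4 has results and statistical analyses presented monthly. At stake is whether a positive primary finding carries the 5% error rate and 80% power that a reader will attach to it.

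**Working it through.** **1. The plan's own figure.** Section 11.2: 33 × 1.20 = 39.6, rounded up to 40. This reproduces. The 33 cannot be checked, because its inputs are in a figure that is not in the text available. As worded, it serves one comparison at 5%.

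**2. Size of the family.**
- Full list (synopsis, 4.2, 5.1): 9 + 4 = 13 headings. IL6, CRP and CK add 2 and the second thermal scale adds 1, giving 16 variables. This is a minimum. Section 5.1 measures skin temperature at five sensor sites and by infrared camera, places conduction velocity under MVIC, and mentions blood pressure under heart rate, without saying how each reduces to one variable.
- Synopsis Objective: 6 headings, or 6 + 2 = 8 variables.
- Outcomes that 5.1 measures at 24-72 h, leaving out skin and core temperature: 7 headings, or 7 + 2 = 9 variables.

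**3. Chance of at least one false positive.** Assume one two-sided test per outcome at 0.05 and no true effect on any outcome.
- Independent: 1 − 0.95^k. For example, 1 − 0.95^6 = 0.265 and 1 − 0.95^16 = 0.560.
- Equal correlation ρ: 1 − ∫[Φ((1.96 − √ρ·u)/√(1−ρ)) − Φ((−1.96 − √ρ·u)/√(1−ρ))]^k φ(u) du, integrated numerically. The values of ρ are assumptions.

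| Family | k | Independent | ρ = 0.5 | ρ = 0.9 |
|---|---|---|---|---|
| Objective, headings | 6 | 26% | 21% | 11% |
| Objective, variables | 8 | 34% | 25% | 12% |
| 24-72 h in 5.1, headings | 7 | 30% | 23% | 11% |
| 24-72 h in 5.1, variables | 9 | 37% | 27% | 12% |
| Full list, headings | 13 | 49% | 33% | 14% |
| Full list, variables | 16 | 56% | 37% | 15% |

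Simulation with 10 per group, closer to the planned model, agrees. At ρ = 0.9 and k = 13 to 16, four-group F tests give 15-16% and group-by-time F tests give 16-17%.

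**4. Favourable reading A: hot water must exceed all three groups.** With no true effect, the chance per outcome is 0.0050 (one-sided 0.05 each, normal approximation) or 0.0016 (two-sided).
- One-sided, independent outcomes: 1 − 0.9950^13 = 6.3%, and 7.6% for 16.
- Two-sided: 2.1% and 2.5%.
- With t tests at the planned sizes, the overall range is about 2-9%.
- If hot water truly beats two groups clearly and equals the third on every outcome, each outcome carries 0.025 or 0.05 again. The independent rates return to 28-33% or 49-56%.

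**5. Favourable reading B: one joint multivariate test must be significant first.** The rate is 5% if nothing differs anywhere. Once any outcome truly differs, the remaining outcomes are unprotected (weak control only). A full multivariate group-by-time test on 16 variables and 4 time contrasts has 16 × 4 = 64 dimensions, against error degrees of freedom of 33 − 4 = 29, 40 − 4 = 36 or 60 − 4 = 56. It could not be run at any sample size in the protocol.

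**6. Power if every variable stays in one Holm family.** Assume a four-group F test with 80% power at 33 and 0.05: noncentrality 12.48, f = √(12.48/33) = 0.615. At the strictest step, 0.05/16 = 0.003125, power is 39% at 33, 54% at 40 and 84% at 60 complete data sets.

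**The case against.** **The outcomes are correlated.** They probably are, but the documents give no value. Even 0.9 across measures as unlike as CK, heart rate and soreness leaves at least twice the nominal 5%.

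**The full list overstates the family.** This stands in part. Skin temperature and thermal sensation after a 10°C or 40°C bath, and blood saturation when jumping under hypoxia, come close to checks that the exposure worked, so a no-effect assumption is artificial there. Timing narrows the list as well. For blood saturation, 5.1 says "This measurement takes place during the baseline measurements as well as during the jump protocol". For breathlessness and exhaustion it says "The measurement takes place before the intervention". Yet 11.1 states hypotheses over 72 hours for all three, and the flow chart lists blood saturation and Borg at follow-up. The Objective family is therefore the fairer headline, and it still exceeds 5% throughout.

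**The plan may intend reading A or B.** Both are possible. Neither 11.4.2 nor the synopsis states either as a decision rule, and both protect only when nothing differs anywhere.

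**This is exploratory physiology.** The synopsis and 2.2 do call it basic physiological research, and an exploratory label for the whole trial would be legitimate. The plan does not apply one: it calls the outcomes primary, states formal hypotheses, claims 80% power and, in 3.1, aims at recommendations.

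**Stronger readings that go too far.** A reader might take 49-56% as this trial's error rate. That needs independence, the widest family and no true effect anywhere, none of which the documents establish. A reader might also test each of the five synopsis pairs alone at 0.05, giving about 18% for one outcome and 92-93% for 13 independent ones (41-44% at 0.9). The synopsis lists those pairs under a factor of the model. No text says that each is a stand-alone decision without an overall test or correction.

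**Conclusion.** The point holds and must be fixed. The plan is silent on multiplicity rather than declaring that none will be applied, but as written it does not hold 5% over its primary hypotheses. For the synopsis Objective list the rate is 26-34% if independent and 11-12% at correlation 0.9. For the full list it is 49-56% and 14-15%. These figures assume one test per outcome, no true effect on any outcome, and correlations that are not in the documents.

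It would be wrong to say that only the all-three reading could bring the rate near 5%, since a joint MANOVA read as a first hurdle would also do so under the same no-effect assumption. What the documents support is that neither protection has been adopted.

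**What to change.** **Primary.** In 4.2, 5.1, 11.1 and 11.4.2, name one primary outcome. Use the G*Power outcome if it is a single outcome on the synopsis Objective list. Otherwise choose one from that list (if inflammation, one named marker). Tie the power statement to it. Name one contrast with its test and time window, saying whether 0 h is included, tested at 0.05.

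**Secondary.** First define one variable for each remaining outcome: skin temperature over sites and devices, MVIC force versus conduction velocity, each blood marker, each thermal scale, and whether blood pressure is an outcome. Then apply Holm to one pre-specified p-value per variable. Use the group-by-time test where measurements repeat, and a between-group test where there is only one time point, as for modified Borg in the flow chart. Adjust pairwise comparisons within an outcome.

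**Decision rules.** State in 11.4.2 whether a claim needs hot water to exceed all three groups, and whether any MANOVA test must be passed first. Reconcile the assessment times in 5.1 with the flow chart.

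**Timing.** File the choice, dated, before any results by group are seen. Section 11.4.2 places the analysis after all data collection and 6.2.2 blinds the statistician, so this should be feasible. However, version 06 (28.09.2021) falls within the planned May-December 2021 data collection, so the date needs documenting. If it is too late, either apply Holm over the closed list of variables, at the power cost in step 6, or label all outcomes exploratory, and report this under 11.4.6.

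**Cost.** Protocol wording, a registry update and, if treated as substantial under 10.4, ethics approval. No extra participants or measurements. The downside is that fewer outcomes can be claimed as confirmatory.
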